10.1.1 Relevant Subset

All patients are in a single arm.

10.1.2 RECIST v1.1

10.1.2.1 Disease Parameters

Measurable disease: Measurable lesions are defined as those that can be accurately measured in at least one dimension (longest diameter to be recorded) as >20 mm by chest x-ray, as >10 mm with CT scan, or >10 mm with calipers by clinical exam. All tumor measurements must be recorded in millimeters.

Note: Tumor lesions that are situated in a previously irradiated area will not be considered measurable unless progression is documented, or a biopsy is obtained to confirm persistence at least 90 days following completion of radiation therapy.

Malignant lymph nodes: To be considered pathologically enlarged and measurable, a lymph node must be >15 mm in short axis when assessed by CT scan (CT scan slice thickness recommended to be no greater than 5 mm). At baseline and in follow-up, only the short axis will be measured and followed.

Non-measurable disease: All other lesions (or sites of disease), including small lesions (longest diameter <10 mm or pathological lymph nodes with ≥ 10 to <15 mm short axis), are considered non-measurable disease. Bone lesions, leptomeningeal disease, ascites, pleural/pericardial effusions, lymphangitis cutis/pulmonitis, inflammatory breast disease, and abdominal masses (not followed by CT or MRI), are considered as non-measurable.

Note: Cystic lesions that meet the criteria for radiographically defined simple cysts should not be considered as malignant lesions (neither measurable nor non-measurable) since they are, by definition, simple cysts. 'Cystic lesions' thought to represent cystic metastases can be considered as measurable lesions, if they meet the definition of

measurability described above. However, if non-cystic lesions are present in the same patient, these are preferred for selection as target lesions.

Target lesions: All measurable lesions up to a maximum of 2 lesions per organ and 5 lesions in total, representative of all involved organs, should be identified as **target lesions** and recorded and measured at baseline. Target lesions should be selected on the basis of their size (lesions with the longest diameter), be representative of all involved organs, but in addition should be those that lend themselves to reproducible repeated measurements. It may be the case that, on occasion, the largest lesion does not lend itself to reproducible measurement in which circumstance the next largest lesion which can be measured reproducibly should be selected. A sum of the diameters (longest for non-nodal lesions, short axis for nodal lesions) for all target lesions will be calculated and reported as the baseline sum diameters. If lymph nodes are to be included in the sum, then only the short axis is added into the sum. The baseline sum diameters will be used as reference to further characterize any objective tumor regression in the measurable dimension of the disease.

Non-target lesions. All other lesions (or sites of disease) including any non-measurable as well as measurable lesions over and above the 5 target lesions should be identified as non-target lesions and should also be recorded at baseline. Measurements of these lesions are not required, but the presence, absence, or in rare cases unequivocal progression of each should be noted throughout follow-up.

10.1.2.2 Methods for Evaluation of Disease

All measurements should be taken and recorded in metric notation using a ruler or calipers. All baseline evaluations should be performed as closely as possible to the beginning of treatment and never more than 6 weeks before the beginning of the treatment.

The same method of assessment and the same technique should be used to characterize each identified and reported lesion at baseline and during follow-up. Imaging-based evaluation is preferred to evaluation by clinical examination unless the lesion(s) being followed cannot be imaged but are assessable by clinical exam.

Clinical lesions: Clinical lesions will only be considered measurable when they are superficial (e.g., skin nodules and palpable lymph nodes) and ≥ 10 mm diameter as assessed using calipers (e.g., skin nodules). In the case of skin lesions, documentation by color photography, including a ruler to estimate the size of the lesion, is recommended.

Chest x-ray: Lesions on chest x-ray are acceptable as measurable lesions when they are clearly defined and surrounded by aerated lung. However, CT is preferable.

Conventional CT and MRI: This guideline has defined measurability of lesions on CT scan based on the assumption that CT slice thickness is 5 mm or less. If CT scans have slice thickness greater than 5 mm, the minimum size for a measurable lesion should be twice the slice thickness. MRI is also acceptable in certain situations (e.g. for body scans), but NOT lung.

FDG-PET: It is sometimes reasonable to incorporate the use of FDG-PET scanning to complement CT scanning in assessment of progression (particularly possible

'new' disease). New lesions on the basis of FDG-PET imaging can be identified according to the following algorithm:

- a. Negative FDG-PET at baseline, with a positive FDG-PET at follow-up is a sign of PD based on a new lesion.
- b. No FDG-PET at baseline and a positive FDG-PET at follow-up: If the positive FDG- PET at follow-up corresponds to a new site of disease confirmed by CT, this is PD. If the positive FDG-PET at follow-up is not confirmed as a new site of disease on CT, additional follow-up CT scans are needed to determine if there is truly progression occurring at that site (if so, the date of PD will be the date of the initial abnormal FDG- PET scan). If the positive FDG-PET at follow-up corresponds to a pre-existing site of disease on CT that is not progressing on the basis of the anatomic images, this is not PD.

10.1.2.3 Response Criteria

Determination of response should take into consideration all target and non-target lesions.

Evaluation of Target Lesions

Complete Response (CR): Disappearance of all target lesions. Any pathological lymph nodes

(whether target or non-target) must have reduction in short axis to <10 mm.

Partial Response (PR): At least a 30% decrease in the sum of the diameters of target lesions, taking as reference the baseline sum diameters.

Progressive Disease (PD): At least a 20% increase in the sum of the diameters of target lesions, taking as reference the smallest sum on study (this includes the baseline sum if that is the smallest on study). In addition to the relative increase of 20%, the sum must also demonstrate an absolute increase of at least 5 mm. (Note: the appearance of one or more new lesions is also considered progressions).

Stable Disease (SD): Neither sufficient shrinkage to qualify for PR nor sufficient increase to qualify for PD, taking as reference the smallest mm diameters while on study.

Not Evaluable (NE): When at least one target lesion is not evaluated at a particular time point.

Evaluation of Non-Target Lesions

Complete Response (CR): Disappearance of all non-target lesions. All lymph nodes must be non-pathological in size (<10 mm short axis).

Non-CR/Non-PD: Persistence of one or more non-target lesion(s).

Progressive Disease (PD): Appearance of one or more new lesions and/or unequivocal progression of existing non-target lesions. Unequivocal progression should normally trump target lesions status. It must be representative of overall disease status change, not a single lesion increase.

Not Evaluable (NE): When at least one non-target lesion is not evaluated at a particular time point.

Although a clear progression of “non-target” lesions only is exceptional, the opinion of the treating physician should prevail in such circumstances.

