10.1.2.5 Best Overall Confirmed Response

Confirmation of CR and PR for determination of best overall response is required for studies with a primary endpoint that includes response.

Time Point Response First time	Time Point Response Subsequent time point ≥ 4 weeks from first time point	BEST overall confirmed response
C	CR	CR
C	PR	SD, PD or PR*
C R	SD	SD provided minimum criteria for SD duration met, otherwise, PD
C R	PD	SD provided minimum criteria for SD duration met, otherwise, PD
C R	NE	SD provided minimum criteria for SD duration met, otherwise, PD
P	CR	PR
P	PR	PR
P	SD	SD
P R	PD	SD provided minimum criteria for SD duration met, otherwise, PD
P R	NE	SD provided minimum criteria for SD duration met, otherwise, NE
N	NE	NE

*If a CR is *truly* met at first time point, then any disease seen at a subsequent time point, even disease meeting PR criteria relative to baseline, makes the disease PD at that point (since disease must have reappeared after CR). However, sometimes ‘CR’ may be claimed when subsequent scans suggest small lesions were likely still present and in fact the patient had PR or SD, not CR at the first time point. Under these circumstances, the original CR should be changed to PR or SD and the best response is PR or SD. PR as best overall response requires ≥ 4 weeks confirmation.

Patients with a global deterioration of health status requiring discontinuation of treatment or die without objective evidence of disease progression at that time should be reported to be off study treatment due to “symptomatic deterioration.” Every effort should be made to document the objective progression even after discontinuation of

treatment.

10.1.2.6 Duration of Response:

Duration of overall response: The duration of overall response is measured from the time measurement criteria are met for CR or PR (whichever is first recorded) until the first date that recurrent or progressive disease is objectively documented (taking as reference for progressive disease the smallest measurements recorded since the treatment started).

The duration of overall CR is measured from the time measurement criteria are first met for CR until the first date that progressive disease is objectively documented.

Duration of stable disease: Stable disease is measured from the start of the treatment until the criteria for progression are met, taking as reference the smallest measurements recorded since the treatment started, including the baseline measurements.

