Progressive Disease (irPD)	
Minimum 20% increase and minimum 5 mm absolute increase in TMTB compared to nadir, or irPD for non-target or new non-measurable lesions. Confirmation of progression is recommended minimum 4 weeks after the first irPD assessment. An irPD confirmation scan may be recommended for subjects with a minimal TMTB %-increase over 20% and especially during the flare time-window of the first 12 weeks of treatment, depending on the compound efficacy expectations, to account for expected delayed response.
 
 • In irRECIST a substantial and unequivocal increase of non-target lesions is indicative of progression. • IrPD may be assigned for a subject with multiple new non-measurable lesions if they are considered to be a sign of unequivocal massive worsening
Other	
irNE: used in exceptional cases where insufficient data exist.
 
irND: in adjuvant setting when no disease is detected
 
irNN: no target disease was identified at baseline, and at follow-up the subject

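### Two not-evaluable (NE) rules need a minor correction: PD shown by the measured target lesions has no stated precedence over NE, and CR followed by NE can fall through to PD

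*Combined protocol and SAP*

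**What the plan says.** Section 10.1.2.3 of the combined protocol and SAP defines target-lesion PD by two thresholds. One is relative: "At least a 20% increase in the sum of the diameters of target lesions, taking as reference the smallest sum on study". The other is absolute: "the sum must also demonstrate an absolute increase of at least 5 mm". The same list defines the unevaluable state: "Not Evaluable (NE): When at least one target lesion is not evaluated at a particular time point". The only ranking it gives concerns non-target disease: "Unequivocal progression should normally trump target lesions status". New lesions also count as progression. There is no table that combines target, non-target and new-lesion status into one time-point response.

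The table in section 10.1.2.5 then pairs a first scan with a later one to give the confirmed best response. For CR followed by NE it says "SD provided minimum criteria for SD duration met, otherwise, PD". For PR followed by NE it says "SD provided minimum criteria for SD duration met, otherwise, NE". Its footnote adds that once a CR is truly met, any disease seen later is PD. Section 10.1.2.6 starts the SD clock: "Stable disease is measured from the start of the treatment until the criteria for progression are met". No minimum SD duration is given in either document part.

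**The concern.** A scan can meet the PD and NE definitions at once, with nothing to say which prevails. Two assessors following the text could score the same images differently. Missed lesions are foreseeable, because section 10.1.4 leaves the choice of scans to the attending physician.

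The endpoint most exposed is duration of response. It is a secondary endpoint (section 12.4) with Kaplan-Meier estimates (section 12.4.2), and it ends at objectively documented progression (section 10.1.2.6). If PD is recorded as NE, the end date moves to a later scan. The best-response window of section 10.1.2.4, which closes at progression, also stays open.

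The table raises a second problem. In one branch it gives a patient a best response of PD when the later scan showed nothing that could be assessed. The equivalent PR row does not do this, and no reason is offered.

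**Working it through.** **The plan's own precision figure (section 12.5).** This is the only design figure that these rules could touch. Wilson interval: centre (p + z²/2n)/(1 + z²/n), half-width z·√(p(1−p)/n + z²/4n²)/(1 + z²/n). With p = 6/30 = 0.20, n = 30 and z = 1.96, the half-width is 13.9 points and the interval 9.5% to 37.3%, as stated. The half-width is 15.13% at 8 responders and 15.61% at 9, and P(X ≤ 8) for a binomial with n = 30 and rate 0.20 is 0.871, matching the stated 87%. Both figures reproduce and are not in dispute.

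**Step 1. Can a partly measured scan prove PD?** Let N be the smallest sum on study, M the sum of the lesions measured now, and m the unmeasured diameter. The true sum is M + m with m ≥ 0. If M ≥ 1.2N and M − N ≥ 5 mm, both PD thresholds are met for every possible m.

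Illustration with assumed sizes: three target lesions, N = 60 mm. Two now measure 45 + 30 = 75 mm and the third is missed.

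| Third lesion (mm) | Sum (mm) | Change from 60 mm |
|---|---|---|
| 0 | 75 | +25%, +15 mm |
| 10 | 85 | +42%, +25 mm |
| 20 | 95 | +58%, +35 mm |

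Every row is PD, yet the NE sentence also applies. With five target lesions and N = 100 mm, four measured lesions averaging 120/4 = 30 mm are enough.

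The converse also holds. If the two lesions measured 40 + 25 = 65 mm, PD would depend on whether the third reached 1.2 × 60 − 65 = 7 mm, and NE would be the right call.

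**Step 2. What is already covered?** New lesions and unequivocal non-target progression give PD despite a missed target lesion. Reappearance after a true CR is PD under the table footnote. What remains is mainly patients with PR or SD whose progression is growth of target lesions only.

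**Step 3. Size of a late date.** Section 10.1 asks for scans at least every 3 months (± 1) for two years and every 6 months (± 1) in years 3-4, counted from the last pembrolizumab dose. Taking the NE scan as on schedule, the next is 3 ± 1 = 2-4 months or 6 ± 1 = 5-7 months later. At the planning rate there are 0.20 × 30 = 6 responders, so one shifted date would be visible on the curve.

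**Step 4. The table rows side by side.**

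| First scan | Later scan | SD minimum met | SD minimum not met |
|---|---|---|---|
| CR | NE | SD | PD |
| PR | NE | SD | NE |
| PR | PD | SD | PD |

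Only the last column separates the two NE rows. An NE scan need show neither the 20% and 5 mm increase nor a new lesion, so the PD in the first row does not follow from section 10.1.2.3.

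**Step 5. Who reaches that branch?** Doses fall at weeks 1, 4, 7 and 10 (section 9), and the end-of-treatment scan is 3 weeks (± 1) after the last dose. After k doses it falls about 3(k − 1) + 3 = 3k weeks from Day 1, ignoring the dosing window. Four doses give 12 weeks (11-13); one dose gives 3 weeks (2-4). With an assumed SD minimum anywhere from 4 to 11 weeks, the four-dose patient is SD. The one-dose patient could fall through.

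**Step 6. Effect of the row change on proportions.** CR then NE can end only as SD, PD or NE, and PR then NE only as SD or NE. Neither is a confirmed CR or PR. Replacing PD by NE in one cell moves patients between two categories that both lie outside CR, PR and SD. The analysis population (section 12.3.1) depends on treatment received, not evaluability, so 6/30 stays 20.0% (9.5% to 37.3%).

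**The case against.** The best defence is that section 10.1.2.3 never says NE overrides PD. The definitions overlap, and a sensible assessor would call PD. That is right: a reader might infer an explicit override, but the text shows only an unranked conflict. The conflict still needs a rule. Section 10.1 cites the published response guideline, but whether that source settles the ranking cannot be checked from these documents.

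Other stronger readings also fail:

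- **PR then NE simply becomes NE, so the two rows are opposite.** Both give SD first; only the fall-through differs.
- **CR then NE creates a false progression date.** The table assigns a best-response category. Duration of response ends only at objectively documented progression, so no date arises.
- **The primary complete response rate is biased.** Step 6 shows that the row change moves no such count. Through the precedence gap, a response count could change only if a response followed a PD that had been recorded as NE.
- **irRECIST contradicts the RECIST rule.** Section 10.1.3.3 says "irNE: used in exceptional cases where insufficient data exist", but nothing there says that a missed target lesion is not insufficient data. The protocol scores both systems by design and expects them to differ.

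It is also fair to object that the fall-through is hard to reach, since section 2.2 puts median time to response on pembrolizumab alone at 2.8 months. That limits the size of the second defect, but the branch still cannot be applied reproducibly without the missing minimum.

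**Conclusion.** The point holds as a minor correction. There is no stated precedence when the evaluated target lesions alone prove PD. The CR-then-NE fall-through assigns PD without the evidence that the protocol's own definition requires, and it turns on an undefined SD minimum.

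The practical effect is mainly on duration of response: one late scan interval per affected patient, as in step 3, provided no extra scan is done in between. The table row affects only the split between PD and NE in best response, mainly among patients who stop early. The confirmed CR rate, the CR+PR rate and the precision at 30 patients are not affected by it.

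The lesion sizes and the 4-11 week SD minimum used above are assumptions. How often a target lesion is missed on a progressing scan is not given and is probably low.

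**What to change.** - **Section 10.1.2.3:** state that a time point is PD, not NE, when the evaluated target lesions alone meet both PD thresholds against the smallest sum on study, or when there is a new lesion or unequivocal non-target progression. In all other cases a missed target lesion gives NE.
- **Section 10.1.2.5:** let the CR-then-NE row fall through to NE, as the PR-then-NE row does, and state the minimum SD duration.

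The cost is a few lines of wording and no new data. A few durations of response may become slightly shorter. The change concerns scoring only; section 4.2 leaves discontinuation for progression to the investigator's judgment, and that is untouched.

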10.1.2.4 Evaluation of Best Overall (unconfirmed) Response

The best overall response is the best time point response recorded from the start of the treatment until disease progression/recurrence (taking as reference for progressive disease the smallest sum recorded since baseline). The patient's best response assignment will depend on the achievement of both measurement and confirmation criteria in some circumstances.

10.1.2.5 Best Overall Confirmed Response

Confirmation of CR and PR for determination of best overall response is required for studies with a primary endpoint that includes response.

Time Point Response First time	Time Point Response Subsequent time point ≥ 4 weeks from first time point	BEST overall confirmed response
C	CR	CR
C	PR	SD, PD or PR*
C R	SD	SD provided minimum criteria for SD duration met, otherwise, PD
C R	PD	SD provided minimum criteria for SD duration met, otherwise, PD
C R	NE	SD provided minimum criteria for SD duration met, otherwise, PD
P	CR	PR
P	PR	PR
P	SD	SD
P R	PD	SD provided minimum criteria for SD duration met, otherwise, PD
P R	NE	SD provided minimum criteria for SD duration met, otherwise, NE
N	NE	NE

*If a CR is *truly* met at first time point, then any disease seen at a subsequent time point, even disease meeting PR criteria relative to baseline, makes the disease PD at that point (since disease must have reappeared after CR). However, sometimes ‘CR’ may be claimed when subsequent scans suggest small lesions were likely still present and in fact the patient had PR or SD, not CR at the first time point. Under these circumstances, the original CR should be changed to PR or SD and the best response is PR or SD. PR as best overall response requires ≥ 4 weeks confirmation.

Patients with a global deterioration of health status requiring discontinuation of treatment or die without objective evidence of disease progression at that time should be reported to be off study treatment due to “symptomatic deterioration.” Every effort should be made to document the objective progression even after discontinuation of

treatment.

10.1.2.6 Duration of Response:

Duration of overall response: The duration of overall response is measured from the time measurement criteria are met for CR or PR (whichever is first recorded) until the first date that recurrent or progressive disease is objectively documented (taking as reference for progressive disease the smallest measurements recorded since the treatment started).

The duration of overall CR is measured from the time measurement criteria are first met for CR until the first date that progressive disease is objectively documented.

Duration of stable disease: Stable disease is measured from the start of the treatment until the criteria for progression are met, taking as reference the smallest measurements recorded since the treatment started, including the baseline measurements.

10.1.2.7 Recurrence:

Recurrence is defined as newly evident disease for patients who have no evidence of disease at baseline or progressive disease for patients who have strictly non-measurable disease at baseline.

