1. OBJECTIVES

1.1. Primary Objective

The primary objectives of this study are to assess 1) the safety and 2) efficacy of combining Anti-PD-1/PD-L1 blockade with palliative radiation therapy in patients with Stage IV Merkel Cell Carcinoma. Efficacy for the primary objective will be tumor response rates (CR, PR, SD, irCR, irPR, irSD) at both irradiated and unirradiated sites.

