1.2. Secondary Objectives

Assessment of Overall Survival and disease control rate/duration of response (CR, PR, SD, irCR, irPR, irSD)

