2.4 Study Design and Duration

This is a single institution, single arm, open-label, Phase II treatment study to evaluate the safety and efficacy of palliative radiation therapy combined with pembrolizumab as a means of providing for PD-1/PD-L1 checkpoint blockade in patients with metastatic Merkel Cell Carcinoma as either first line therapy or upon progression on prior therapy.

In this study, pembrolizumab will be administered at 200 mg IV every 3 weeks as standard of care as approved by the FDA. Palliative radiation therapy will be given between the first and second cycles of immunotherapy.

Subject participation in this study comprises the following time periods:

- Screening
 - Screening assesses the subject's eligibility to participate as determined by the inclusion/exclusion criteria.
 - Screening labs and ECOG Performance Status must be completed within 4 weeks of confirmation of eligibility. Imaging must be completed within 4 weeks of confirmation of eligibility and within 6 weeks of starting pembrolizumab therapy.
 - Eligibility must be confirmed within 28 days of signing the informed consent form.

- Pembrolizumab
 - Patients will receive pembrolizumab as a single agent administered 200 mg as standard of care intravenously every 3 weeks until progression or unacceptable toxicity.
 - Laboratory evaluations must be performed and the results examined before administration of each dose.
 - As durable disease stabilization and/or objective tumor response can be seen after early progression before Week 12, it is recommended that, in the absence of dose-limiting toxicities (e.g., serious AEs), immunotherapy be administered over

the initial 12 weeks even in the setting of apparent clinical progression, providing the subject's performance status remains stable.

- All subjects, including those who may have discontinued treatment for drug-related AEs and/or who have evidence of clinical progression, should obtain a tumor assessment 3 weeks (± 1 week) after the last dose of pembrolizumab.

- Based on clinical experience in ongoing and completed immunotherapy studies, the following recommendations apply for subject management in light of the tumor assessment taken 3 weeks (± 1 week) after the last dose of pembrolizumab:

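### The confirmation table turns an unevaluable scan after a CR into PD when the SD minimum is not met, and that minimum, used by five of 11 rows, is never set

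*Combined protocol and SAP*

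**What the plan says.** Section 10.1.2.5 requires CR and PR to be confirmed at least 4 weeks later and gives an 11-row table for the resulting best response. CR then NE reads "SD provided minimum criteria for SD duration met, otherwise, PD". PR then NE reads "SD provided minimum criteria for SD duration met, otherwise, NE". CR then SD, CR then PD and PR then PD also depend on a minimum SD duration. PR then SD carries no such condition.

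Section 10.1.2.3 defines SD by size only: "Neither sufficient shrinkage to qualify for PR nor sufficient increase to qualify for PD, taking as reference the smallest mm diameters while on study". Section 10.1.3.3 defines irSD as what remains when irCR, irPR and irPD are all ruled out, again without a time element. Section 10.1.2.6 measures SD from the start of treatment but sets no minimum.

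SD counts in the objectives. Section 1.1: "Efficacy for the primary objective will be tumor response rates (CR, PR, SD, irCR, irPR, irSD) at both irradiated and unirradiated sites". Section 1.2 adds "disease control rate/duration of response (CR, PR, SD, irCR, irPR, irSD").

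On timing, Section 2.4 says that all subjects, including early stoppers, "should obtain a tumor assessment 3 weeks (± 1 week) after the last dose of pembrolizumab". Section 10.1.4 lists baseline, the end of treatment visit and follow-up visits as the measurement points.

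**The concern.** There are two linked defects. First, the same missing information gives PD after an unconfirmed CR and NE after an unconfirmed PR, so the better first response gets the worse fallback. Second, the table relies on a threshold that does not exist. Someone must supply it later, in an open-label single-arm trial, possibly with the scans already in view. Two analysts could then report different disease control rates from identical data.

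The scan schedule adds to the second problem. The first scan is tied to the last dose, so without a floor the SD label covers very different lengths of observation.

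**Working it through.** **1. The five rows that use the minimum.**

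| First scan | Next scan | Result if the minimum is not met | What the next scan shows |
|---|---|---|---|
| CR | SD | PD | disease present again |
| CR | PD | PD | progression |
| CR | NE | PD | nothing assessable |
| PR | PD | PD | progression |
| PR | NE | NE | nothing assessable |

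In three of the four rows ending in PD, the fallback rests on something seen; the table's footnote explains why disease seen after a true CR is PD. Only CR then NE has no observation behind it. Section 10.1.2.3 requires for PD a 20% and 5 mm increase, a new lesion, or unequivocal non-target progression, and it labels an unevaluated lesion NE. Section 10.1.2.6 ends a response only when progression is objectively recorded. The CR-then-NE fallback conflicts with all of these.

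**2. Where SD has no floor.** No row starts from SD. A patient whose first scan shows SD is governed by Section 10.1.2.3 and by the best time-point rule in Section 10.1.2.4, neither of which sets a minimum time.

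**3. When SD can first be scored.** Inputs: Day 1 is the first dose; dosing is every 3 weeks with a -3/+7 day window (Section 4); the scan is 14 to 28 days after the last dose (Section 2.4); radiation falls between cycles 1 and 2 (Section 5.1.2). One dose plus completed radiation places a patient in the analysis population (Sections 12.3.1 and 12.4.1).

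- One dose: 14 to 28 days after Day 1.
- Four doses, nominal (Days 1, 22, 43, 64): scan on Day 64 + 14 = 78 to Day 64 + 28 = 92, which is 77 to 91 days after Day 1.
- Fourth dose alone 3 days early (Day 61): earliest scan Day 75, which is 74 days after Day 1.
- Every interval 3 days short (Days 1, 19, 37, 55): earliest scan Day 69, which is 68 days after Day 1.

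Four doses is one scenario. Treatment may continue until progression or toxicity, so the spread can be wider.

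**4. Effect on the rates.** One patient is 1/30 = 3.3 points, taking 30 analysed patients with NE kept in the denominator. The documents give no expected disease control rate. With an assumed 20/30, Wilson 95% intervals are:

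| Controlled | Rate | 95% CI |
|---|---|---|
| 20/30 | 66.7% | 48.8% to 80.8% |
| 19/30 | 63.3% | 45.5% to 78.1% |
| 18/30 | 60.0% | 42.3% to 75.4% |
| 17/30 | 56.7% | 39.2% to 72.6% |

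**5. What does not move.** Section 12.5 reproduces. For 6/30, with z = 1.96, the Wilson centre is (0.2 + z²/60)/(1 + z²/30) = 0.234 and the half-width is 0.139, giving 9.5% to 37.3%. The half-width is 15.13% at 8/30 and 15.61% at 9/30, so the chance that it is at most 15.5% is P(X ≤ 8 | 30, 0.20) = 0.871, the stated 87%. The futility rule stops with probability 0.8^15 + 15 × 0.2 × 0.8^14 = 0.167 at a 20% response rate. SD, PD and NE are all non-CR and non-PR, so neither defect touches these figures.

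**The case against.** The strongest reply is that little of the formal analysis depends on this. Section 12.3 names the complete response rate as primary endpoint, Section 12.2 counts only PR or CR, and Section 12.4 does not list disease control. That is right and it limits the point. It does not remove it, because Sections 1.1 and 1.2 still count SD and irSD. Whether SD belongs in the primary objective at all is a separate inconsistency.

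A second reply is that early stoppers are imaged again at least every 3 months (Sections 4 and 10.1), so one who stays stable would qualify under any reasonable floor. This also largely stands. A floor removes only those whose early SD is followed by PD, or by no evaluable scan, before a qualifying assessment. The documents are not uniform here: Section 2.4 places patients who stop for toxicity in survival follow-up, which collects survival status only.

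A reader might infer a large effect by applying the 14% treatment-related discontinuation in Section 2.2 to 30 patients (0.14 × 30 = 4.2, or 14 points). The documents do not support that. The figure comes from pembrolizumab alone over a median follow-up of 14.9 months. It does not describe stopping after one dose, it says nothing about unchanged tumours, and it ignores later scans.

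A reader might also take 77 days as the natural floor, or as a Week 13 scan. Week 13 appears only for the thyroid test, and the dosing window puts a compliant four-dose scan as early as 68 to 74 days.

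**Conclusion.** The CR-then-NE fallback is wrong as written, because it contradicts the protocol's own definitions of PD and NE. Its reach is narrow: it affects only the PD/NE split of best response, and only when the minimum is not met. With a floor of 68 days or less, a four-dose patient meets the minimum at the first scan. The PD branch then needs an early stopper with a CR and then an unevaluable scan, so probably few patients. It would be too strong to say that the table always converts CR then NE into progression, since the row gives SD when the minimum is met.

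The missing SD minimum is a real gap in the disease control rate and in any rate that includes SD. It is worth 3.3 points per reclassified patient, and the number of patients is unknown. It would also be too strong to say that best-response categories in general will be wrong: CR and PR assignments are unaffected. The two defects interact, because setting a minimum without correcting the CR-then-NE row is what brings its PD fallback into use.

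**What to change.** 1. In Section 10.1.2.5, change the CR-then-NE entry to match PR then NE: "SD provided minimum criteria for SD duration met, otherwise, NE".
2. Before the data are analysed, state one minimum interval from Day 1 for SD and irSD as best response. The study team should choose the value. It should let every compliant four-dose end of treatment scan qualify, which means no more than 68 days; 77 would exclude some.
3. Apply that interval in Sections 10.1.2.3, 10.1.2.5 and 10.1.3.3 and in the definition of disease control. State whether the PR-then-SD row carries it too.
4. Class a patient whose only SD assessment falls before the minimum, with no later qualifying scan and no PD, as NE, and keep that patient in the denominator.

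The cost is a few lines of text. Sample size, visits and treatment do not change. The small downside is a slightly lower disease control rate.
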